2 STUDY OBJECTIVES

The primary objective of this study is to assess the efficacy of repeated oral doses of serlopitant in adult subjects with chronic pruritus of unknown origin.

The secondary objective of this study is to assess the safety and tolerability of repeated oral doses of serlopitant in adult subjects with chronic pruritus of unknown origin.

3 STUDY DESIGN

3.1 Overall Study Design

This is a double-blind, randomized, placebo-controlled study to assess the efficacy, safety, and tolerability of serlopitant for the treatment of chronic pruritus of unknown origin. Approximately 200 subjects who meet the study entry criteria will be randomized in a 1:1 ratio to receive daily oral doses of serlopitant 5 mg or placebo for 10 weeks. After completion of the treatment period or early discontinuation of study drug treatment, all subjects will enter a 5-week follow-up period.

This study will consist of three periods, for a total study period of 18 weeks:

- Screening period: 3 weeks
- Treatment period: 10 weeks
- Follow-up period: 5 weeks

Informed consent will occur prior to any protocol-mandated procedures, including the stopping of any excluded therapies. This may occur prior to the Screening visit.

During the screening period, all subjects will undergo eligibility evaluation and will be assessed for conditions associated with chronic pruritus. If the investigator deems that additional assessments are necessary to rule out specific conditions based on a subject's history, physical examination, and/or screening labs (e.g. scabies skin preparations, urea breath test for *Helicobacter pylori*), the subject may not be randomized until these are completed and the pruritus is still considered to be of unknown origin.

Subjects will be provided an eDiary at the Screening visit. Subjects must be willing and able to complete the eDiary every day within a consistent 6-hour timeframe, and comply with restrictions on allowable concomitant therapies, for the duration of the study. eDiary compliance and WI-NRS scores will be used to determine study eligibility (see [Section 4.1](#)).

At the Baseline visit (Day 1), eligible subjects will be randomly assigned to receive study drug (serlopitant 5 mg or placebo). Subjects will take a loading dose (3 tablets taken orally) at the site on the first day of the treatment period (Day 1). Starting on Day 2, subjects will take one tablet per day until the completion of the 10-week treatment period. Study drug may be taken with or without food.

After the last dose of study drug, all subjects will enter a 5-week follow-up period and will undergo a follow-up visit at the conclusion of the follow-up period. The eDiary will continue to be completed during the follow-up period.

The primary efficacy endpoint will be assessed at Week 10 of treatment.

3.2 Rationale for Study Design and Dose Selection

In the TCP-102 study in patients with PN, serlopitant 5 mg taken daily for 8 weeks was superior to placebo for the reduction of pruritus, in both the overall study population as well as the subgroup of subjects with an atopic diathesis. Similarly, in the TCP-101 study in patients with chronic pruritus, serlopitant 5 mg and 1 mg taken daily for 6 weeks were superior to placebo for the reduction of pruritus, in both the overall study population and the subgroup of subjects with an atopic diathesis.

In both the TCP-102 and TCP-101 studies, serlopitant was generally well-tolerated and demonstrated an overall favorable safety profile at the doses evaluated.

The current MTI-117 study is designed to investigate the efficacy, safety, and tolerability of serlopitant for the treatment of chronic pruritus of unknown origin. The 5 mg dose of serlopitant was selected for this study based on a combination of human central nervous system positron emission tomography receptor occupancy (RO) data for serlopitant generated in healthy young males (Study P002), which showed a serlopitant 4 mg LFC (equivalent to a 5 mg tablet) once daily dose is likely to achieve ~ 94% NK₁ RO at steady state, together with results of studies TCP-101 and TCP-102 that demonstrated a favorable efficacy, safety, and tolerability profile of serlopitant at this dose level in subjects with pruritus. Over 250 subjects have been exposed to serlopitant at doses of 5 mg tablet-equivalent daily for at least 6 weeks, and ~ 40 subjects have been exposed up to one year.

3.3 Study Endpoints

3.3.1 Primary Efficacy Endpoint

The primary efficacy endpoint is the Worst-Itch Numeric Rating Scale (WI-NRS) 4-point responder rate at Week 10.

3.3.2 Secondary Efficacy Endpoints

The secondary efficacy endpoints are as follows:

- WI-NRS 4-point responder rate at Weeks 2, 4, 6, and 8
- WI-NRS 3-point responder rate at Weeks 2, 4, 6, 8, and 10
- Change from baseline in WI-NRS at Weeks 2, 4, 6, 8, and 10
- Change from baseline in daily WI-NRS scores through Week 2
- Change from baseline in WI-VAS at Weeks 2, 4, 6, and 10

3.3.3 Safety Endpoints

Safety endpoints are as follows:

- Incidence of TEAEs and SAEs
- Changes from baseline in clinical laboratory parameters following study drug exposure
- Changes from baseline in vital sign and ECG parameters following study drug exposure
- Plasma concentrations of serlopitant and metabolites

3.3.4 Exploratory Endpoints

The exploratory endpoints are as follows:

- Change from baseline in the Epworth Sleepiness Scale (ESS) to Weeks 2, 4, 6, and 10
- Change from baseline in Static Patient Global Assessment of Itch Severity (sPGA) to Weeks 2, 4, 6, and 10
- Patient Global Impression of Change in Itch Severity (PGIC) at Weeks 2, 4, 6, and 10

3.4 Safety Review

3.4.1 Safety Monitoring Team

An internal safety monitoring team consisting of representatives from Menlo Therapeutics Inc. and its designees will monitor blinded safety data on a regular basis throughout the study.

4 SELECTION OF STUDY POPULATION

4.1 Study Population

Approximately 200 adult subjects with chronic pruritus of unknown origin will be enrolled in this study.

4.2 Inclusion Criteria

Subjects must meet the following criteria to be randomized into the study:

1. Male or female, age 18 years or older at consent.
2. The subject must have had ongoing pruritus for at least 6 months.
3. The subject's pruritus is assessed by the investigator to be of unknown origin at baseline.
4. The pruritus must have been unresponsive to prior treatment with emollients.
5. The pruritus must involve more than one dermatome (defined as an area of skin in which sensory nerves derive from a single spinal nerve root). Acceptable examples include right and left arm, occipital and frontal scalp, and upper and lower back.
6. Worst-Itch Numeric Rating Scale (WI-NRS) score ≥ 7 in the 24-hour period prior to the Screening visit
7. Average weekly Worst Itch Numeric Rating Scale (WI-NRS) score ≥ 7 in the week (7 days) immediately prior to randomization, as recorded in the eDiary.
8. Willing and able to complete daily eDiary entries within a consistent timeframe for the duration of the study, as demonstrated by a $\geq 80\%$ eDiary completion rate in the two weeks immediately prior to randomization.

9. All females who are of childbearing potential must be willing to practice highly effective contraception (i.e., pregnancy prevention method with a failure rate of < 1% per year) from the time of the Screening visit until 5 weeks after last study dosing.
10. Adequate cognitive and physical ability, in the investigator's opinion, to comply with study visits and study related requirements including providing written informed consent.

4.3 Exclusion Criteria

Subjects who meet any of the following criteria are not eligible for participation in the study:

1. Prior treatment with serlopitant or any other neurokinin-1 receptor antagonist.
2. Known dermatologic or systemic condition(s), other than dry skin, that is considered by the investigator to be the primary cause of current pruritus .
3. Untreated or inadequately treated thyroid, adrenal, or pituitary disease or nodules, or history of thyroid malignancy.
4. Use of an excluded therapy within 3 weeks prior to randomization (see [Section 5.7](#))
5. Treatment with any investigational therapy within 3 weeks prior to randomization.
6. Serum creatinine, total bilirubin, alanine aminotransferase or aspartate aminotransferase > 2.5 times the upper limit of normal during screening.
7. History of malignancy within 3 years prior to randomization, with the exception of actinic keratosis or completely treated and non-metastatic cutaneous squamous cell carcinoma or basal cell carcinoma of the skin.
8. Any known major psychiatric diagnosis which, in the investigator's opinion, may confound the assessment of serlopitant safety or efficacy or interfere with the subject's ability to comply with protocol-mandated activities.
9. Suicidal ideation within 3 years prior to randomization, or any history of suicide attempt.
10. Known use of recreational drugs.
11. Documented history of parasitic infection, including skin parasites such as scabies, within 12 weeks prior to randomization.
12. Presence of clinically significant dementia, intellectual impairment, or any medical condition or disability that, in the investigator's opinion, could interfere with the assessment of safety or efficacy in this trial or compromise the safety of the subject.
13. History of hypersensitivity to serlopitant or any of its components.
14. Planned or anticipated major surgical procedure or other activity that would interfere with the subject's ability to comply with protocol-mandated assessments (e.g. extended international travel) during the subject's participation in the study.
15. Pregnant or breastfeeding female.

5 STUDY DRUG

5.1 Study Drug Supply, Route of Administration, and Storage

The study drug in this study is serlopitant 5 mg or placebo in a film-coated tablet formulation for oral administration. The serlopitant tablets contain microcrystalline cellulose, mannitol, croscarmellose sodium, silicon dioxide, sodium lauryl sulfate, and magnesium stearate, and are film coated with Opadry® Brown. The placebo tablets contain microcrystalline cellulose, lactose monohydrate, and magnesium stearate, and are film coated with Opadry® Brown.

The study drug will be provided in bottles for storage at room temperature (59–86°F, 15–30°C).

Each bottle provided will include 18 tablets. One bottle will be issued via Interactive Web Response System (IWRS) at each of Baseline, Week 2, and Week 4, and two bottles will be issued via IWRS at Week 6. A total of 5 bottles will be dispensed to subjects completing 10 weeks of study drug treatment.

Additional details regarding study drug supplies can be found in the Pharmacy Manual.

5.2 Labeling and Study Drug Accountability

The study drug will be appropriately packaged and labeled in bottles with 18 tablets per bottle. The study drug supplied for this study is not to be used for any purpose other than this study, and study drug accountability must be maintained for all bottles distributed to the investigative site.

Additional details regarding study drug labeling and accountability can be found in the Pharmacy Manual.

5.3 Dosing Regimen

Subjects will take a loading dose (3 tablets taken orally) at the site on the first day of the treatment period (Study Day 1). Starting on Study Day 2, subjects will be instructed to take one tablet per day orally until completion of the 10-week treatment period. Study drug may be taken with or without food.

5.4 Dose Modification

No dose modification of study drug will be allowed during this study.

5.5 Missed or Delayed Doses

Each dose of study drug after the first dose must be administered as a single tablet daily. If a dose is missed, that dose will be documented as a missed dose. Dosing should resume the next day as only a single tablet, as per protocol dosing instructions (i.e. there should be no attempt to make up for the missed dose).

5.6 Study Drug Discontinuation

Subjects should be discontinued from study drug treatment in the following situations:

- A female subject desires to become pregnant at the current time, stops contraception or expels her intrauterine device/implant, or becomes pregnant
- A female subject has new breast findings (e.g. a palpable mass or abnormal mammography, discharge), or has abnormal vaginal discharge or bleeding
- The subject decides to discontinue study drug treatment, or withdraws consent from the study
- The subject receives a strong CYP3A4 inhibitor (See [Appendix B](#))
- Any medical condition that may jeopardize the subject's safety if study drug is continued, in the investigator's and/or Sponsor's opinion; this may include the development of persistently (2 successive occasions) abnormal thyroid function tests (TSH >10, or TSH > 6 with low free T4; TSH < 0.1, or TSH < 0.35 with high free T4); abnormal morning prolactin, cortisol, or corticotropin levels; or signs and symptoms of adrenal insufficiency
- Discontinuation is deemed to be in the best interest of the subject, in the investigator's and/or Sponsor's opinion, including evidence that the subject does not meet inclusion/exclusion criteria intended primarily for safety reasons, or a persistent lack of adherence to study procedures

The Sponsor or designee should be contacted within 24 hours of investigator's awareness of any study drug treatment discontinuation. Investigators should make every effort to contact the Sponsor or designee before discontinuing study drug treatment, if possible.

Subjects who discontinue treatment with study drug prior to completing the treatment period will enter a 5-week follow-up period following the last dose of study drug and will have a Follow-up visit (see [Section 3.1](#), [Section 6.5.10](#)). Every effort should be made for subjects to complete the Follow-up visit after a subject has discontinued from study drug.

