1.3 Serlopitant

1.3.1 Serlopitant Background and Nonclinical Summary

Serlopitant is a small molecule, highly selective NK₁-R antagonist that is administered orally and metabolized by cytochrome P-450 3A4 (CYP3A4), with a plasma half-life of 45–86 hours. It binds with high affinity to the human NK₁-R with a dissociation constant (K_d) of 46 pM; displacing SP binding with a half-maximal inhibition concentration (IC₅₀) of 61 pM. Serlopitant is a potent functional antagonist of SP-induced inositol phosphate generation.

Serlopitant has been extensively studied in animal toxicology studies, including chronic toxicology and carcinogenicity studies. In non-clinical chronic toxicology studies in rats, mice and dogs, treatment related findings of potential clinical significance included increased salivation, decreased body weight gain and food consumption, slight changes in hematology and serum biochemistry parameters, mild increases in liver weight and mild histomorphologic changes. The histomorphologic changes were seen only in rats (not in dogs or mice) and included: very slight ovarian interstitial cell hypertrophy, mammary gland and uterine atrophy; decreased corpora lutea; increased histiocytes in lung and mesenteric lymph nodes; slight skeletal and cardiac muscle degeneration; slight increased hematopoiesis in bone marrow; and slight to moderate vacuolation in kidney tubules. These nonclinical findings occurred at systemic exposures exceeding those anticipated to provide efficacy of serlopitant for pruritus indications in humans (1 to 5 mg tablet daily). No cardiac lesions have

been observed in dog toxicity studies up to 9 months in duration nor in a 3-month mouse range-finding study and 2-year mouse carcinogenicity study at exposure higher than the lowest level which caused cardiotoxicity in rats. The no observed adverse effect level (NOAEL) in rats for histomorphological changes in the reproductive tract, mammary gland and bone marrow provides a 2.5-fold margin for the maximum-targeted exposure (5 mg tablet daily). The rat NOAEL for histomorphological changes in muscle and kidney provides a 5-fold margin for the maximum-targeted exposure (5 mg tablet daily).

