6.3 Pharmacokinetic Measurements

Sparse PK sampling will involve collecting one PK sample at the week 10 visit according to the schedule in [Appendix A](#). The date and time of dosing prior to PK sample collection and date and time of PK sample collection will be recorded. The plasma concentrations of serlopitant and metabolites M1/M1a, M2/M2a and M3 will be determined and data used for population PK analysis. Detailed instructions regarding PK sample collection, preparation, and shipment can be found in the laboratory manual.

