- Confirm next scheduled visit

6.5.10 *Week 10 Visit*

The Week 10 visit occurs 70 days (+ 3 days) after the Baseline visit. At the Week 10 visit, the following procedures and assessments are to be performed:

- Ask the subject to complete the WI-VAS, ESS, sPGA, and PGIC questionnaires
- Assess and record any changes in the subject's concomitant medications
- Female subjects should be queried for presence of new breast masses or abnormal discharge, and abnormal vaginal bleeding or discharge
- Assess and record any AEs and SAEs
- Obtain vital signs
- Perform a urine pregnancy test for females of childbearing potential and confirm the subject has a negative urine pregnancy test result prior to randomization (with positive or equivocal results confirmed by a serum pregnancy test)
- Draw blood for clinical laboratory tests (morning blood sampling due to Endocrine assessments)
 - Reproductive endocrine labs for females under 55 years of age at consent who are not using hormonal contraception or other hormonal therapies at Screening
 - Endocrine
 - Hematology
 - Chemistry
- Collect PK blood sample
- Perform targeted physical examination, including weight
- Review study drug compliance
- Collect returned study drug
- Review eDiary for compliance, re-train subject as needed
- Confirm next scheduled visit

6.5.11 *Follow-up Visit*

The required Follow-up visit occurs 35 days (+7 days) after the Week 10 visit or the last dose of study drug (for subjects who discontinue study drug early).

At the Follow-up visit, the following procedures and assessments are to be performed:

- Register visit into the IWRS

- Ask the subject to complete the WI-VAS, ESS, sPGA, and PGIC questionnaires
- Assess and record any changes in the subject's concomitant medications
- Female subjects should be queried for presence of new breast masses or abnormal discharge, and abnormal vaginal bleeding or discharge
- Obtain ECG
- Obtain vital signs
- Perform targeted physical examination, including weight
- Perform a urine pregnancy test for females of childbearing potential (with positive or equivocal results confirmed by a serum pregnancy test)
- Draw blood for clinical laboratory tests (morning blood sampling due to Endocrine assessments)
 - Reproductive endocrine labs for females under 55 years of age at consent who are not using hormonal contraception or other hormonal therapies at Screening
 - Endocrine
 - Hematology
 - Chemistry
- Assess and record any AEs and SAEs

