- Collect eDiary device, review eDiary for compliance

6.5.12 *Early Termination From the Study*

Early termination of a subject from the study may occur due to loss to follow-up, withdrawal of consent by the subject. In accordance with legal requirements and International Council on Harmonization (ICH) –GCP guidelines, every subject or his/her legal representative has the right to withdraw from the study at any time and without providing reasons. If provided, the reason (adverse event, study burden, lack of efficacy, other) a subject withdrew consent will be recorded in the electronic Case Report Form (eCRF). The PI or site staff must make every effort to contact subjects who are suspected of being lost to follow-up. Attempts to contact such subjects must be documented in the subject's source documents.

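### Subjects who stop study drug early have no scheduled safety assessment at stopping, and the SAP windows can report their off-drug Follow-up values as Week 6 or Week 10

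*Protocol*

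**What the plan says.** Protocol Section 3.1 sets one path for everyone: "After completion of the treatment period or early discontinuation of study drug treatment, all subjects will enter a 5-week follow-up period". Section 5.6 repeats it for early stoppers: "Subjects who discontinue treatment with study drug prior to completing the treatment period will enter a 5-week follow-up period following the last dose". It names only a Follow-up visit, but its cross-reference is to Section 6.5.10, which is the Week 10 visit. The Follow-up visit is Section 6.5.11, and it "occurs 35 days (+7 days) after the Week 10 visit or the last dose of study drug (for subjects who discontinue study drug early".

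The schedule in Appendix A (Table 2) has no column for early discontinuation or end of treatment. Section 6.5.12, on early termination, opens with "Early termination of a subject from the study may occur due to loss to follow-up" and goes on to reasons for leaving and attempts at contact. It lists no procedures.

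The Week 10 laboratory, endocrine and PK set is tied to a visit 70 (+3) days after Baseline. The endocrine panel is scheduled only at Screening, Week 10 and Follow-up (Section 6.2.3). On PK, Section 6.3 says "Sparse PK sampling will involve collecting one PK sample at the week 10 visit". Section 3.3.3 lists plasma concentrations of serlopitant and its metabolites among the safety endpoints.

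SAP Section 2.4 assigns visit-based data by study day. In Table 3, Week 6 is Day 36 to 57 and Week 10 is any day after Day 57. The SAP defines Follow-Up separately, as the last assessment at least seven days after the end of treatment. SAP Sections 3.5.2 and 3.5.4 tabulate laboratory and ECG results by these windows.

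**The concern.** Subjects who stop because of an adverse event are among the most informative for safety. For them, the protocol schedules no measurement close to the time of stopping. A reversible laboratory effect could have resolved by the one visit they are required to attend, and that visit cannot supply an on-drug value.

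Two features of this protocol sharpen the point. Section 5.6 names thyroid, prolactin, cortisol and corticotropin abnormalities as possible grounds for stopping, yet nobody has a scheduled on-treatment endocrine sample before Week 10. It also lists receipt of a strong CYP3A4 inhibitor as a reason to stop. Section 1.3.1 says that CYP3A4 metabolizes the drug, but no PK sample is scheduled at that moment.

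The SAP adds an analysis problem. Its windows have no on-treatment limit, so values taken weeks after the last dose can be summarized under an on-treatment week label. That would dilute any laboratory signal in the later weeks.

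**Working it through.** The documents give no residual-drug figure and no expected number of early stoppers, so there is no plan figure to reproduce.

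**Step 1. What is scheduled (Protocol Sections 6.2, 6.3, 6.5.4 to 6.5.12; Appendix A, Table 2).**

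| Assessment | Scheduled on treatment | Next scheduled after an early stop |
|---|---|---|
| Hematology, chemistry | Weeks 4, 10 | Follow-up |
| Endocrine, reproductive endocrine | Week 10 | Follow-up |
| PK sample | Week 10 | None |
| ECG | Week 4 | Follow-up |
| Vital signs | Weeks 2, 4, 6, 10 | Follow-up |
| Targeted exam | Weeks 4, 6, 10 | Follow-up |

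A subject who stops before the Week 4 visit therefore has no scheduled on-drug hematology, chemistry, ECG, endocrine or PK value. One who stops between Weeks 4 and 10 has the Week 4 hematology, chemistry and ECG, but no scheduled on-drug endocrine or PK value.

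**Step 2. Parent drug left at the Follow-up visit.** Section 1.3.1 describes serlopitant "with a plasma half-life of 45–86 hours". Assuming first-order elimination, the fraction of the last-dose level remaining is 2^(−t/h), where t is the time since the last dose and h is the half-life. The visit falls at 35 × 24 = 840 h to 42 × 24 = 1008 h.

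| Time since last dose | h = 86 h | h = 45 h |
|---|---|---|
| 35 days | 840/86 = 9.77 half-lives, 0.115% | 840/45 = 18.67 half-lives, 0.00024% |
| 42 days | 1008/86 = 11.72 half-lives, 0.030% | 1008/45 = 22.4 half-lives, 0.000018% |

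For contrast only, 7 days after the last dose (168 h) the fraction is 2^(−168/86) = 26% or 2^(−168/45) = 7.5%.

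**Step 3. How many subjects.** In TCP-102 (Section 1.3.3), 128 subjects were randomized 1:1, so about 64 per arm. The reported 71.9% of serlopitant subjects with a TEAE agrees with this, since 46/64 = 71.9%. Nine subjects discontinued for TEAEs: 3 on serlopitant and 6 on placebo. The serlopitant rate is 3/64 = 4.7%, or about 5 of the 100 serlopitant subjects planned here. Scaling from 8 to 10 weeks at a constant rate gives 4.7% × 10/8 = 5.9%, or about 6. The documents give no rate for stops for other reasons.

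**Step 4. Where the Follow-up visit falls in SAP Table 3.** With the last dose on study Day s, the visit is on Day s + 35 to s + 42.

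| Last dose | Follow-up visit | Table 3 window |
|---|---|---|
| Day 1 | Day 36 to 43 | Week 6 |
| Day 14 | Day 49 to 56 | Week 6 |
| Day 22 | Day 57 to 64 | Week 6 or Week 10 |
| Day 23 | Day 58 to 65 | Week 10 |
| Day 42 | Day 77 to 84 | Week 10 |

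From a last dose on Day 23 (23 + 35 = 58) onward, the visit always falls in the Week 10 window. Completers are protected because the assessment closest to target Day 71 is used, and their Week 10 visit is closer than their Follow-up visit. An early stopper who has left the on-treatment schedule has no such competing value. The same off-drug result then appears under Week 10 as well as Follow-Up.

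**The case against.** The protocol does not leave stoppers unobserved. Sections 6.2.1 to 6.2.4 allow vital signs, examination, laboratory tests and ECG at unscheduled visits when clinically indicated, and an adverse event leading to a stop is an obvious occasion. The sponsor is to be contacted within 24 hours of awareness of any discontinuation (Section 5.6). Adverse events are sought at each contact and followed until resolved or stable (Sections 7.2.2 and 7.3). Protocol Section 8.9.2 summarizes out-of-range laboratory values at any post-baseline assessment, so an abnormal unscheduled result would be captured. A stop triggered by endocrine results presupposes that those results exist. All of this stands. It limits the claim to scheduled or required assessments, but it does not answer it: unscheduled testing is at the investigator's discretion, is not uniform across sites and is not tied to stopping.

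Four stronger readings are tempting, and the documents do not support them:

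- **That stoppers have no safety measurement at all.** The provisions above contradict this, and many stoppers will have on-treatment vital signs and Week 4 laboratory values.
- **That about 14 of 200 subjects would be affected on drug**, from 9/128 = 7.0% × 200. Six of those nine were on placebo and had no drug to measure.
- **That early stoppers are singled out for a missing end-of-treatment ECG.** Completers have no Week 10 ECG either. Only subjects who stop before Week 4 lose an on-treatment ECG.
- **That nothing active remains at Follow-up.** The calculation covers parent drug only. Section 1.3.2 reports three long-lived active metabolites and gives no half-life for them. A washout visit can also still detect a lasting effect.

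The 5.6 cross-reference may simply be a stale section number. Even so, a site cannot tell from the text whether the Week 10 set was intended.

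**Conclusion.** The point holds in this form. At early discontinuation nothing is scheduled or required, and the next scheduled hematology, chemistry and endocrine tests come 35 to 42 days after the last dose, with parent drug at 0.115% or less. No early stopper has a scheduled on-drug endocrine or PK value.

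The number affected is modest: about 5 of 100 serlopitant subjects stopping for a TEAE, plus an unknown number stopping for other reasons. That figure rests on three events in an 8-week study of prurigo nodularis and gives only an order of magnitude. The residual-drug figure assumes first-order elimination within the stated half-life range.

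The window problem follows directly from SAP Table 3. It affects stoppers in both arms whose Follow-up visit is their only assessment in the Week 6 or Week 10 window. The documents also need to square a thyroid criterion of two successive abnormal occasions with a schedule that has one on-treatment endocrine sample. When drug should be stopped is outside this point.

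**What to change.** **Protocol.** Reconcile Section 5.6 (including its reference to 6.5.10) with Sections 6.5.10, 6.5.11 and 6.5.12 and Appendix A. They should state plainly whether the already-defined Week 10 laboratory, endocrine and PK set applies at early discontinuation. Timing is for the sponsor to set, and the 35-day Follow-up visit stays.

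**SAP.** Report any such values as end of treatment. For safety data, limit the Table 3 post-baseline windows to on-treatment assessments, so that a Follow-up value is summarized only as Follow-Up. One workable boundary is the seven days after end of treatment that Section 2.4 already uses to define Follow-Up. It would keep completers' Week 10 visits, which fall within a few days of the last dose. How the same windows should treat the visit-based questionnaires is a separate question.

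**Cost.** If the set is applied, early stoppers have one visit in place of on-treatment visits they no longer attend, and some will decline it. Completers have no added visit. Appendix A and the eCRF change. The late on-treatment windows will hold fewer values, because the off-drug ones are removed.
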